A Pragmatic Randomized Multiple Baseline Trial Evaluating Knowledge Insight Tools (KIT), a Cognitive Behavioural Therapy-informed School-based Counselling Intervention for Secondary School-aged Children and Young People with Anxiety and Mood Difficulties in the UK

Statistical Analysis Plans

NCT ID: Not yet assignment

Document Date: 01/08/2023

Statistical methods

Statistical methods for primary and secondary outcomes {20a}

Primary Outcome

The primary outcome is YP-CORE scores, assessed weekly throughout the baseline and intervention phases. We will analyze within-person and between-person change in YP-CORE scores using descriptive and inferential statistics suitable for multiple baseline designs.

Descriptive methods include summary statistics (e.g., measures of central tendency and dispersion) and visual analysis, where we will inspect time-series graphs of session-by-session scores for stability during the baseline phase, negative trends in the intervention phase, variability within and between phases, and the general degree of overlap between baseline and intervention scores using range lines (Lane & Gast, 2014).

Inferential methods include piecewise multilevel growth models to estimate within-person and between-person differences in average scores (i.e. levels) and the direction/rate of change in scores (i.e. slopes) between the baseline and intervention phases (e.g., Reut et al., 2023). Models will include at least two levels, with repeated observations of YP-CORE scores at level 1 nested within each young person at level 2. We will include additional levels if there is significant variation associated with specific therapists, schools, or regions. We will estimate fixed effects, which include intercepts and slopes averaged across young people for both the baseline and intervention phases (see below for piecewise coding of phases). We will also estimate random effects, which include between-person variation in intercepts and slopes for the baseline and intervention phases.

Two dummy-coded variables each representing an intercept for the baseline phase and intervention phase will be included in the model at level one. Each intercept variable will be coded to reflect the individually-varying break-points between baseline and intervention phases. Take, for instance, a young person with a three-

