week baseline phase followed by a four-week intervention phase. The baseline intercept variable for this young person would be coded as 1, 1, 1, 0, 0, 0, 0, and the intervention intercept variable as 0, 0, 0, 1, 1, 1, 1. This coding will produce estimates of the mean baseline and intervention YP-CORE scores averaged across young people with individually varying phase lengths. Baseline and intervention intercepts can then be compared using a two-tailed Wald test to estimate a treatment effect; mean YP-CORE scores during the intervention phase are predicted to be significantly lower than mean YP-CORE scores during the baseline phase.

Two more dummy-coded variables will be included at level one to estimate the slopes for the baseline and intervention phases. The baseline slope variable will be coded for the weeks until the first intervention session, whilst the intervention slope variable will be coded for the weeks since the first intervention session. Continuing the example above of a young person with a three-week baseline phase and four-week intervention phase, the baseline slope variable would be coded as -3, -2, -1, 0, 0, 0, 0, and the intervention slope variable would be coded as 0, 0, 0, 0, 1, 2, 3. Note that the first intervention session is coded as a '0' across baseline and intervention time variables because it serves as the pre-treatment baseline (since the YP-CORE will be administered at the beginning of the first intervention session, before the intervention starts). This coding will produce estimates of the mean slopes during the baseline and intervention phases; a baseline slope not significantly different from zero, plus a significant negative intervention slope, would indicate a treatment effect. Furthermore, random intercepts and slopes will allow us to quantify stability and intraindividual variability in YP-CORE trajectories that would be observed in the visual analysis.

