Between-person covariates, including the randomly allocated start week, absolute time in weeks since the first participant was recruited, age, sex, ethnicity, free school-meal eligibility, and special education needs status, will be added to level two of the model to control for the confounding effects of method variables and demographics. We will also include interactions within time variables to investigate non-linear trajectories in YP-CORE scores, and interactions between time and demographic variables to investigate whether demographics moderate the treatment effect.

Multilevel models tend to be robust to deviations from their parametric assumptions (Maas & Hox, 2004). However, we will explore non-parametric alternatives, like Simulation Modelling Analysis (e.g., Dunn et al., 2019), if our data heavily violate these assumptions.

We will also estimate treatment effects and their effect size in line with standard outcomes reported in randomized controlled trials. For the treatment effect, we will use randomization tests, which, unlike more common tests of repeated measures like paired *t*-tests, do not make distributional assumptions or assume homogeneous variances (Bulté & Onghena, 2009). This is because the sampling distribution is based on random permutations of the observed data (i.e. a randomization distribution). We will also calculate a measure of effect size: Shadish et al.'s (2014) adapted *d*-statistic for single-case designs or Tau-U if there are trends in the baseline phase (Manolov, Losada, Chacón-Moscoso, & Sanduvete-Chaves, 2016).

Secondary Outcomes

Secondary outcomes include the RCADS, KIT Fidelity Checklist, and Implementation Survey. The RCADS will be completed at the start, middle and end of the intervention. We will use measures of central tendency and dispersion (e.g., means and standard deviations) to report group-level differences in scores between the baseline and intervention phases. Furthermore, we will evaluate the statistical significance of the difference in group means using parametric tests (e.g., repeated *t*-test), non-parametric (e.g., Wilcoxon Signed-rank test) tests, and regression models controlling for covariates, and quantify the size of the difference using the standardized mean difference (i.e. Cohen's *d*).

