The Fidelity Checklist will be scored in various ways. Traditionally, clinical researchers calculate an index of the proportion of practitioners demonstrating a prespecified level of treatment fidelity. For each KIT intervention with a young person, we will calculate proportions of completeness for each KIT phase across sessions and a total completeness score. That is, we will score the presence of each item on the checklist as a '1' and calculate the proportion of items scored within each phase. Only the first instance of the item throughout the intervention will be counted, not the frequency of the item across sessions. We will also create a total score by summing the subscale scores together. We will then determine a threshold for a 'complete' KIT intervention (e.g., scoring at least 75% of items within each subscale, across all subscales), and determine the proportion of KIT interventions meeting this threshold. This will allow us to conduct sensitivity analyses with complete KIT interventions only vs. incomplete KIT interventions. Since fidelity data will be assessed over time, we can also control for session-by-session fidelity scores in the multilevel growth models of YP-CORE trajectories or analyze patterns/profiles of scores on the fidelity checklists that predict better outcomes.

As for the Implementation Survey, we will use measures of central tendency and dispersion to get an overall sense of how practitioners experienced implementing

KIT. We will also examine the distribution of responses for each item to determine what practitioners favoured most/least about KIT. Some questions, e.g., confidence around delivering KIT, can be used as moderators in the multilevel growth curve models. Depending on the number and richness of responses, we will analyze free-text responses with thematic analysis to draw out practitioners' views of the advantages and barriers to delivering KIT.

Interim analyses {21b}

We will estimate the sample's conditional power after recruiting 50% of the target ($N = 30$) or if we have not met our recruitment target by the first deadline (February 2024), whichever comes first. If the conditional power estimate indicates that we need more participants than the initial target of 60, we will extend recruitment to a second wave with an adjusted alpha level for subsequent analyses.

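### The slope criterion for the primary outcome reads a KIT effect from two separate significance verdicts and names no test of whether the two slopes differ

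*SAP*

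**What the plan says.** The SAP, under Statistical methods for primary and secondary outcomes {20a}, Primary Outcome, fits a piecewise multilevel model with a separate intercept and slope for each phase. In general terms it says the model will estimate differences in level and in "the direction/rate of change in scores (i.e. slopes) between the baseline and intervention phases". It then fixes how the estimates are to be read:

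- **Levels:** "Baseline and intervention intercepts can then be compared using a two-tailed Wald test to estimate a treatment effect".
- **Slopes:** "a baseline slope not significantly different from zero, plus a significant negative intervention slope, would indicate a treatment effect".

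The level comparison has a named test. The slope comparison has none; it consists of one verdict per phase. The coding is illustrated with "a young person with a three-week baseline phase and four-week intervention phase".

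Further on, the same section adds "For the treatment effect, we will use randomization tests" and "We will also include interactions within time variables to investigate non-linear trajectories in YP-CORE scores". The slope criterion is not made conditional on the level test or on the randomization test.

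**The concern.** One significant and one non-significant result do not show that two quantities differ. A non-significant baseline slope can mean no trend, or a trend measured too imprecisely to detect. The less informative the baseline, the easier the first half of the criterion is to satisfy.

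The baseline phase exists to separate KIT from change that was already under way. As worded, the slope sentence would allow a report to claim an effect on the primary outcome from a decline that did not alter when KIT started. Absolute time since first recruitment is a planned covariate, but it enters at level two, between persons, so it does not remove a weekly trend within a person.

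**Working it through.** The SAP gives no error rate or power for the slope criterion, so there is no figure of its own to reproduce.

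**1. Precision in the SAP's own example.** Baseline times -3, -2, -1 have a within-person sum of squares of 2. Intervention times 0, 1, 2, 3 have 5. Without random slopes, the baseline slope's standard error is √(5/2) = 1.58 times that of the intervention slope.

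**2. Inputs.** From the SAP: the coding, random intercepts and slopes, and N = 60 (Interim analyses {21b}). Assumed, because the SAP gives no values: two-sided α = 0.05, residual SD 4, person SD 5, slope SD 0.4 points per week (independent in the two phases), baselines of 3 to 6 weeks in equal numbers, 6 sessions. The truth is set to the same linear trend in both phases, with no KIT effect.

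**3. Standard errors.** From (ΣX′V⁻¹X)⁻¹: baseline slope 0.183, intervention slope 0.134, difference √(0.183² + 0.134²) = 0.227 points per week. The two slope estimates are uncorrelated.

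**4. Probability that the criterion is met.** P(|z_baseline| < 1.96) × P(z_intervention < -1.96). At a shared trend of -0.3 per week:

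- Baseline: mean z = -0.3/0.183 = -1.64, so P(not significant) = Φ(3.60) - Φ(-0.32) ≈ 0.625.
- Intervention: mean z = -0.3/0.134 = -2.24, so P(significant decline) = Φ(0.28) ≈ 0.610.
- Product: 0.625 × 0.610 = 0.38.

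| Shared trend (points/week) | 0 | -0.1 | -0.2 | -0.3 | -0.5 | -0.75 | -1.0 |
|---|---|---|---|---|---|---|---|
| 3 to 6 weeks, 6 sessions | 2.4% | 10% | 26% | 38% | 21% | 1.6% | 0% |
| SAP's 3 + 4 example for everyone | 2.4% | 5.8% | 12% | 21% | 41% | 42% | 22% |

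The nominal rate towards benefit is 2.5%. In the first row the peak is 39% at -0.33, and the rate exceeds 5% only for trends from about -0.05 to -0.65.

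**5. Sensitivity of the peak.**

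- 3 to 6 week baselines: about 16% with 4 sessions, 65% with 10.
- 6 sessions: 26% with 3 to 8 week baselines, 18% with 6 to 8 weeks, 12% with 8 to 10 weeks.
- 6 to 8 week baselines with 4 sessions: 7%.
- Residual SD 3 to 6 and slope SD 0.2 to 0.8 (3 to 6 weeks, 6 sessions): the peak stays at 35 to 39%, at trends of roughly -0.25 to -0.5 per week.

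**6. The direct contrast.** The Wald test of the slope difference rejects in 5.0% of trials (2.5% towards benefit) at every shared linear trend.

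**7. Check by simulation.** In 100 simulated trials with fitted mixed models (3 + 4 weeks, shared trend -0.6, slope SD 0.3), the criterion was met in 44% and the slope contrast rejected in 5% (Monte Carlo error about 5 and 2 percentage points).

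**The case against.** The strongest reply is that the slope sentence is only one line of evidence. The SAP says in general terms that slope differences are estimated, and the model would yield the contrast. It also plans visual inspection of baseline stability, a level test, randomization tests, and Tau-U as the effect size if there are baseline trends. Under a shared linear trend, the slope criterion and the level test would both favour KIT in under 2% of trials (3 to 6 weeks, 6 sessions), so a false slope reading would usually sit beside a null level test. This limits the harm. It does not repair the sentence, because the SAP neither requires agreement nor says which result governs.

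A second reply is that the size is assumed. The 3 + 4 week case only illustrates coding, phase lengths may be set in the protocol, and longer baselines shrink the problem. That stands for the size, not for the logic.

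A third reply is that the contrast has its own weaknesses: lower power, and a bias towards harm when natural improvement slows. Both are real and are costed under the fix. They call for care in reading the contrast; they do not make two separate verdicts a valid comparison.

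**Conclusion.** The concern holds. The slope sentence is wrong as written: it treats a difference between two verdicts as evidence of a difference between slopes, and the SAP names no test of that difference. The model itself is suitable.

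The error matters for modest shared trends. With no trend the criterion keeps its nominal rate, and with a steep trend the baseline slope becomes significant and the criterion is rarely met. In between, under the assumptions above, the false-positive rate peaks at 39%, and at 7% to 65% over the other phase lengths tried. The direction is firm. The size depends on variances, phase lengths and a natural trend that the SAP does not give.

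**What to change.** In {20a}, Primary Outcome, replace the slope sentence with:

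> *The change in slope at the start of KIT will be tested with a two-sided Wald test of (intervention slope - baseline slope) = 0 from the piecewise model and reported with its 95% confidence interval. The separate baseline and intervention slopes will be reported descriptively.*

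Add that this contrast removes only a linear trend common to both phases and will be interpreted together with the non-linear time terms already planned.

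No new data or model are needed. There are three costs:

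1. **Power.** Suppose the baseline is truly flat and the slope changes by -0.5 per week (3 to 6 weeks, 6 sessions). The present criterion is met with probability 0.95 × Φ(0.5/0.134 - 1.96) ≈ 0.95 × 0.962 = 91%. The contrast has Φ(0.5/0.227 - 1.96) = 60%. For 80% power, N ≈ 60 × [(1.96 + 0.84) × 0.227/0.5]² ≈ 97. With 4 sessions it is about 169, with 10 about 74.
2. **Interim step.** Interim analyses {21b} says "We will estimate the sample's conditional power after recruiting 50% of the target". It must state whether conditional power refers to this contrast.
3. **Decelerating natural improvement.** Assume exponential improvement of 4 to 6 points in total at a rate of 0.2 to 0.4 per week, with no KIT effect. The contrast then signals benefit in under 0.1% of trials but rejects towards harm in 26 to 97%. A quadratic intervention-time term cuts this to 6 to 32%. The present criterion is met in 0 to 7% of such trials. A rejection towards harm should therefore not be read without the non-linear check.

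### The SAP says random intercepts and slopes will measure intraindividual variability, but they measure differences between young people; weekly fluctuation is the level-1 residual, which the SAP never mentions

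*SAP*

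**What the plan says.** All of this is in the SAP, Statistical methods for primary and secondary outcomes {20a}, Primary Outcome.

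- The visual analysis is to inspect "stability during the baseline phase, negative trends in the intervention phase, variability within and between phases", as well as overlap between the phases.
- The growth model has "repeated observations of YP-CORE scores at level 1 nested within each young person at level 2".
- Its random effects are introduced as follows: "We will also estimate random effects, which include between-person variation in intercepts and slopes for the baseline and intervention phases".
- After the phase coding has been set out, the SAP adds that "random intercepts and slopes will allow us to quantify stability and intraindividual variability in YP-CORE trajectories that would be observed in the visual analysis".
- On assumptions, it remarks that "Multilevel models tend to be robust to deviations from their parametric assumptions".

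The level-1 residual does not appear: neither its variance, nor whether that variance is common to both phases, nor whether it will be reported.

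**The concern.** The SAP gives one set of parameters two meanings. It first defines them, correctly, as spread between young people. It then offers them as the model counterpart of the stability and within-person variability seen in the graphs. Two young people with the same level and slope can fluctuate by very different amounts from week to week and still have identical random effects.

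If the sentence were followed, spread between young people would be reported as within-person variability. A real change in volatility between phases would have no parameter of its own, and under a common residual variance part of it could surface as apparent differences in trajectory. Baseline slopes are most exposed, and they are what this design uses to judge whether baselines are stable.

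**Working it through.** The SAP gives no figure on this point, so there is none to reproduce. The check is on the model, followed by simulation.

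**Model.** With the SAP's four level-1 variables (phase dummies B and I, phase times tb and ti), the score of young person i at week j is

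y_ij = b_Bi·B + b_Ii·I + s_Bi·tb + s_Ii·ti + e_ij.

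The variances of b and s across i are between-person quantities. The variance of e_ij is the fluctuation of one person's scores around that person's own line.

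**Inputs.** The target of 60 comes from the SAP (Interim analyses {21b}). Everything else is assumed. All fits are REML with four random effects and, unless stated, one residual variance.

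- Set A: 3–7 baseline and 6–10 intervention scores, person SD 6, baseline-slope SD 0, intervention-slope SD 0.6; 60 trials per setting, root-mean-square SDs.
- Set B: 3–6 baseline and 8 intervention scores, intercept SDs 5 (correlation 0.7), slope SDs 0.5; 20 trials per setting, median SDs.

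| Set | True weekly SD, baseline / intervention | Baseline intercept SD | Intervention intercept SD | Baseline slope SD | Intervention slope SD | Residual SD |
|---|---|---|---|---|---|---|
| A | 2 / 2 | 5.93 | 5.91 | 0.17 | 0.61 | 1.99 |
| A | 6 / 6 | 6.26 | 6.08 | 0.49 | 0.66 | 5.96 |
| A | 6 / 3 | 7.10 | 5.71 | 1.04 | 0.49 | 4.27 |
| A | 3 / 6 | 5.68 | 6.38 | 0.15 | 0.80 | 5.00 |
| B | 2 / 2 | 4.81 | 4.93 | 0.48 | 0.49 | 1.98 |
| B | 4 / 4 | 5.07 | 4.90 | 0.57 | 0.48 | 3.93 |
| B | 4 / 2 | 5.71 | 4.80 | 1.10 | 0.39 | 2.75 |
| B | 2 / 4 | 4.50 | 5.06 | 0.27 | 0.57 | 3.35 |

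**Step 1: which parameter tracks fluctuation?** In set A the weekly SD triples. The intervention-intercept SD rises by 0.17 (5.91 to 6.08) and the intervention-slope SD by 0.05 (0.61 to 0.66), while the residual SD goes from 1.99 to 5.96. The baseline-slope SD rises from 0.17 to 0.49 although its true value is 0. That is boundary bias: an estimated SD cannot fall below zero, so noise pushes it upward. In set B, where the true slope SD is 0.5, doubling the weekly SD leaves the slope SDs at 0.48–0.57 while the residual SD doubles. A refit of set A with 40 trials per setting agreed: intervention intercept 5.93 to 6.03, intervention slope 0.60 to 0.63, residual 1.97 to 5.92.

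**Step 2: what if fluctuation changes with phase?** One residual variance returns roughly an average weighted by number of scores. For set A, taking mid-range lengths of 5 and 8 weeks:

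- SD 6 then 3: √[(5×36 + 8×9)/13] = √19.38 = 4.40; fitted 4.27.
- SD 3 then 6: √[(5×9 + 8×36)/13] = √25.62 = 5.06; fitted 5.00.

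Neither value describes either phase, and the mismatch distorts the random effects. With SD 6 then 3, the baseline-slope SD is 1.04 (1.10 in the 40-trial refit), against 0.49 when both SDs are 6. In set B, where the truth is 0.5, it is 1.10 when fluctuation halves and 0.27 when it doubles.

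**Step 3: do phase-specific residual variances help?** In the 40-trial refit with SD 6 then 3, they cut the baseline-slope SD from 1.10 to 0.53, about the boundary-bias level, and recovered residual SDs of 5.82 and 2.99. With SD 3 then 6, they lowered the standard error of the intercept contrast from 0.77 to 0.64, or 17% (1 − 0.64/0.77).

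**Step 4: are the tests affected?** With no true effect, one residual variance and 150 trials per setting:

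- SD 6 then 3: mean contrast −0.01; rejection at nominal 5% was 4.0% for the contrast and 2.7% for the intervention slope.
- SD 3 then 6: mean contrast 0.02; rejection 0.7% and 4.7%.

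The Monte Carlo standard error at 5% is √(0.05×0.95/150) = 1.8 percentage points. This rules out gross inflation only; the 0.7% indicates a conservative test.

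**The case against.** The strongest reply is that the sentence is loosely worded rather than wrong. It speaks of variability in trajectories. A person's phase slope does show whether that person's baseline is flat, which is one sense of stability, and the gap between a person's two intercepts is within-person change. This stands, and it is why the sentence needs rewording rather than deletion. It does not cover scatter, which the SAP lists for the visual analysis separately from trend.

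Three stronger readings are tempting, and the document does not support them.

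- A reader might infer that the SAP assumes equal residual variance in the two phases. It does not say so; the structure is unspecified. A common variance is only the usual default when nothing else is planned.
- A reader might infer that the trial could not check what the graphs show about variability. The SAP plans measures of dispersion, inspection of "variability within and between phases" and range lines. What is missing is the inferential counterpart that the sentence promises.
- A reader might infer that the treatment-effect tests are invalid. Step 4 shows no bias and no false-positive inflation. The SAP also plans randomization tests, chosen partly because they do not need homogeneous variances, and non-parametric alternatives if assumptions are heavily violated.

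It is also fair to say that nothing in the SAP suggests fluctuation will halve or double between phases. The distortion in step 2 depends on a change of that kind. The mislabelling in step 1 does not.

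**Conclusion.** The concern holds in limited form. The sentence conflicts with the SAP's own definition of the random effects and names the wrong quantity for week-to-week variability. That follows from the model whatever the inputs, and the simulations confirm it.

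The second part is conditional. If fluctuation changes with phase and a single residual variance is fitted, the change is blended into one residual SD and the random-effect SDs are distorted. With SD 6 then 3, the baseline-slope SD is about 1.0–1.1 against about 0.5 from boundary bias alone. These sizes rest on assumed phase lengths and variances; only the 60 comes from the SAP.

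The consequence lies in interpretation and in the variance model. The only effect seen on the tests was lost precision when fluctuation rises. No figure stated in the SAP changes.

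**What to change.** 1. Reword the sentence in {20a} so that random intercepts and slopes describe differences between young people in level and trend. It may keep the point that person-specific slopes and intercept gaps show systematic change.
2. Specify separate level-1 residual variances for baseline and intervention. Report both residual SDs with confidence intervals as the measure of within-person variability, beside the planned graphs.
3. Do not add residual SDs for each young person by phase. In the SAP's own example the baseline has three scores; an individual intercept and slope leave 3 − 2 = 1 residual degree of freedom, too few for a usable estimate.

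The cost is a change of wording and one extra variance parameter in the model. No additional data are needed.

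### Absolute time entered at level two cannot adjust the within-person level and slope contrasts, so non-linear school-calendar effects stay in the piecewise model's estimates

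*SAP*

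**What the plan says.** Under Primary Outcome in section {20a}, the SAP describes a model "with repeated observations of YP-CORE scores at level 1 nested within each young person at level 2". Four level-one variables carry the treatment effect: an intercept and a slope for each phase. Two readouts follow from them. For level, "Baseline and intervention intercepts can then be compared using a two-tailed Wald test to estimate a treatment effect". For slope, "a baseline slope not significantly different from zero, plus a significant negative intervention slope, would indicate a treatment effect".

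Calendar time appears once in the model: "absolute time in weeks since the first participant was recruited" is listed, together with demographics, as one of the between-person covariates that "will be added to level two of the model to control for the confounding effects of method variables and demographics". The planned interactions are among the time variables and between time and demographics. No level-one term for calendar week, term or closure is named. The same section also plans a randomization test for the treatment effect. School closures are mentioned in {20b} and {20c}, but only as a reason why a first session may move.

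**The concern.** In a multiple baseline design, staggered starts exist to separate the effect of treatment from the passage of time. The SAP recognises this by naming absolute time as something to control, but puts it at the level where it carries no information about change within a young person. Both readouts are changes within a young person. If distress rises or falls at some point of the school year, the piecewise model can only attribute that movement to the phase intercepts and slopes, and the level-two covariate does not take it back out. An analyst following the text would believe calendar time had been controlled when, for these contrasts, it had not.

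**Working it through.** **1. The covariate cancels.** For young person j in week t, with phase indicators B and I (B + I = 1 in every row), phase slopes SB and SI, and absolute time C fixed per person:

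y = β_B·B + β_I·I + γ_B·SB + γ_I·SI + δ·C_j + u_j + e

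C_j shifts both phase levels by δ·C_j. The level contrast is (β_I + δ·C_j) − (β_B + δ·C_j) = β_I − β_B, and the slopes γ_B and γ_I do not involve C_j. In the SAP's seven-week example the four phase variables have rank 4, and adding a person-constant column leaves the rank at 4.

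**2. A linear calendar term at level one is no remedy.** In the SAP's example, "the baseline slope variable would be coded as -3, -2, -1, 0, 0, 0, 0". Its counterpart for the second phase takes the value 0 in the first four weeks and then 1, 2, 3. Their sum is -3, -2, -1, 0, 1, 2, 3, which is the week number minus 4. Within a person, linear calendar week is therefore already a combination of the phase variables, and adding it again leaves the rank at 4. It follows that linear drift goes equally into both slopes and cancels from the intercept contrast.

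**3. Simulation with no treatment effect.** From the SAP: target N = 60 (Interim analyses, {21b}) and the phase coding. Assumed: baseline 3 to 8 weeks, 8 intervention weeks, person SD 5, residual SD 4, random-intercept models, 60 replicates per scenario. The level-two terms were entry week and baseline length.

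| Calendar effect, 4-week recruitment | Phase-mean contrast, no calendar term | With level-two terms |
|---|---|---|
| Linear drift, -0.2 a week | -1.389 | -1.390 |
| Step of -2 points | -0.481 | -0.484 |
| Seasonal swing | -3.242 | -3.250 |

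The level-two terms moved the contrast by at most 0.008 here (3.250 − 3.242). With 24-week recruitment the pairs were -1.340 and -1.344 (linear), -0.532 and -0.533 (step), and 0.140 and 0.140 (season).

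In the four-variable piecewise model with level-two terms and 4-week recruitment:
- Linear drift gave slopes of -0.196 (baseline) and -0.191 (intervention), with an intercept contrast of -0.061. The -1.39 in the table arises only when phase means are compared without slopes.
- The step gave a baseline slope of -0.054 and an intervention slope of -0.203 a week, close to the pattern the SAP reads as a treatment effect. Interacting the level-two terms with all phase variables left the intervention slope at -0.214.
- With 24-week recruitment the step gave an intervention slope of -0.077.

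**4. Size for a temporary rise.** Assumed: +3 points for four weeks, baseline 3 to 6 weeks, 8 intervention weeks, entry uniform over the window, weeks counted from 0, no treatment effect.

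| Entry window | Rise in | Spurious intervention slope, per week | Level bias |
|---|---|---|---|
| 4 weeks | weeks 4-7 | about -0.35 (baseline slope about +0.47) | about -0.7 |
| 4 weeks | weeks 10-13 | about +0.35 | not larger |
| 16-24 weeks | either | about -0.08 to -0.02 | up to about 0.2 |

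Timing matters: counting weeks from 1 instead of 0 changes the 4-week level bias for weeks 4-7 from about -0.7 to about -1.3.

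**5. Randomization test.** With no treatment effect, 300 replicates and a fixed observation window, one-sided rejection at nominal 0.05 was 0.033 and 0.037 (linear drift, 4- and 24-week recruitment) and 0.043 and 0.060 (step). The Monte Carlo standard error is √(0.05 × 0.95 / 300) = 0.013, so all are compatible with 0.05.

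**The case against.** Several points on the other side have weight.

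- **Meaning of the covariate.** It can be read as recruitment timing, which is a legitimate level-two adjustment for early versus late recruits. That stands, and is why it should be kept under that label. It does not supply control over calendar change within a person. If a time-varying variable was meant, the text says otherwise, and a linear version would be collinear with the slopes.
- **Randomization test.** It rests on the randomized start weeks and kept its type I error in the simulation. This stands. It protects a p-value, but does not correct the model's slopes, intercept contrast or Wald test.
- **Flat-baseline condition.** It catches part of the problem: linear drift shows in the baseline slope, and so does the rise in weeks 4-7. The protection is partial, because it depends on detecting a non-zero baseline slope and the step scenario largely escapes it.
- **Recruitment spread.** The SAP is dated 01/08/2023 and gives February 2024 as the first recruitment deadline, with a possible second wave. That points to months rather than weeks, where bias from a temporary rise is small. The start and pattern of entry are not stated, so compressed entry cannot be excluded.

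A reader might infer more: that the trial's treatment inference as a whole is confounded with the calendar, or that the error is as large as the slope difference in the compressed case (-0.35 − 0.47 = -0.82 a week). The SAP does not support either reading. It plans no slope-difference test, more than half of that figure is a rising baseline that the flat-baseline condition is meant to flag, and the randomization test remains valid.

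**Conclusion.** The point holds in a limited form. That a level-two value cannot adjust the within-person contrasts follows from the SAP's own coding and needs no assumption. The consequence is confined to the piecewise model's estimates and Wald tests, and to non-linear calendar effects. Its size rests on inputs the SAP does not give: the height, length and timing of the disturbance, the phase lengths and the spread of entry. Under the assumed 3-point, four-week rise it ranges from material with entry inside 4 weeks, in either direction, to minor with entry over 16 to 24 weeks. A lasting step fades less with wider entry: the phase-mean contrast was still biased by about -0.53 at 24 weeks.

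**What to change.** Keep recruitment week at level two, but name it recruitment timing and drop the implication that it controls calendar change within a person. Add to the level-one model, at minimum as a pre-specified sensitivity analysis, a small set of time-varying indicators for calendar periods (for example the weeks adjoining closures). Fix the periods before analysis and code them from each school's own calendar, because schools and regions may differ. Do not use a linear calendar term.

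The cost is a date lookup and a small loss of precision; no new data are needed. With one period indicator and 4-week recruitment, the bias was removed and the SD of the intervention slope went from about 0.09 to 0.09-0.10. That is a favourable case, because the indicator matched the simulated disturbance exactly; effects outside the chosen periods, or specific to a school and not coded, are not removed. Full week-by-week indicators cost more: the SD of the phase-mean contrast rose from about 0.3 to 0.5-0.6 with 4-week recruitment, and from about 0.2-0.4 to 0.4-0.5 with 24-week recruitment.
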